Requesting a waiver of signed consent for the Entire Study (Note that an information sheet may be required.)

If requesting a waiver of signed consent, please address the following:

a. Would the signed consent form be the only record linking the subject and the research?

Yes No

b. Does a breach of confidentiality constitute the principal risk to subjects?

Yes No

OR

c. Does the research pose greater than minimal risk? Yes ***If you answered yes, stop. A waiver cannot be granted.*** No

AND

d. Does the research include any activities that would require signed consent in a non-research context? Yes No

B. Full waiver of consent: (No consent from subjects will be obtained for the activity.)

Requesting a waiver of consent for Recruitment/Screening only

a. Does the research activity pose greater than minimal risk to subjects?

Yes ***If you answered yes, stop. A waiver cannot be granted.*** Please note:

Recruitment/screening is generally a minimal risk research activity

No

b. Will the waiver adversely affect subjects' rights and welfare? Yes No

c. Why would the research be impracticable to conduct without the waiver?

d. Where appropriate, how will pertinent information be returned to, or shared with subjects at a later date?

Requesting a full waiver of consent for the Entire Study (Note: If PHI is collected, information here must match Section VII, question 6.)

If requesting a full waiver of consent, please address the following:

- a. Does the research pose greater than minimal risk to subjects?
 Yes ***If you answered yes, stop. A waiver cannot be granted.***
 No
- b. Will the waiver adversely affect subjects' rights and welfare? Yes No
- c. Why would the research be impracticable to conduct without the waiver?
- d. Where appropriate, how will pertinent information be returned to, or shared with subjects at a later date?

SECTION VIII: PROTECTION OF RESEARCH SUBJECTS

Confidentiality & Security of Data:

- a. What protected health information (medical information along with the HIPAA identifiers) about subjects will be collected and used for the research?
- b. Subject Name, date of birth, and Medical Record number as well as clinical imaging, pathologic and staging information will be collected.
- c. How will the research data be collected, recorded and stored?
All research data will be collected as part of the medical record and stored in a secure ITS managed database (FMS Med). Only co-investigators will be able to collect, record and access this workstation, and no collaborators on this study will have access to PHI.
- d.
- c. How will the digital data be stored? CD DVD Flash Drive Portable Hard Drive Secured Server Laptop Computer Desktop Computer Other
- d. What methods and procedures will be used to safeguard the confidentiality and security of the identifiable study data and the storage media indicated above during and after the subject's participation in the study?

The data will be stored on and ITS managed secure database in the medical school, accessible only by co-investigators

Do all portable devices contain encryption software? Yes No

If no, see <http://hipaa.yale.edu/guidance/policy.html>

- e. What will be done with the data when the research is completed? Are there plans to destroy the identifiable data? If yes, describe how, by whom and when identifiers will be destroyed. If no, describe how the data and/or identifiers will be secured.
All identifies will be secured in an encrypted database.
- f. Who will have access to the protected health information (such as the research sponsor, the investigator, the research staff, all research monitors, FDA, Yale Cancer Center Data and Safety Monitoring Committee (DSMC), SSC, etc.)? (please distinguish between PHI and de-identified data).
PHI will be accessible by co-investigators only, collaborators will not have access
- g. If appropriate, has a [Certificate of Confidentiality](#) been obtained? N/A
- h. Are any of the study procedures likely to yield information subject to mandatory reporting requirements? (e.g. HIV testing – reporting of communicable diseases; parent interview -

incidents of child abuse, elderly abuse, etc.). Please verify to whom such instances will need to be reported. N/A

SECTION IX: POTENTIAL BENEFITS

Potential Benefits: Identify any benefits that may be reasonably expected to result from the research, either to the subject(s) or to society at large. (Payment of subjects is not considered a benefit in this context of the risk benefit assessment.)

Prostate cancer could potentially be discovered at an earlier and more localized stage allowing for greater chance of cure with treatment.

SECTION X: RESEARCH ALTERNATIVES AND ECONOMIC CONSIDERATIONS

1. **Alternatives:** What other alternatives are available to the study subjects outside of the research?
There is no current alternative. Patients may request to be screened for prostate cancer with standard of care management
2. **Payments for Participation (Economic Considerations):** Describe any payments that will be made to subjects, the amount and schedule of payments, and the conditions for receiving this compensation. – no payment for participation
3. **Costs for Participation (Economic Considerations):** Clearly describe the subject's costs associated with participation in the research, and the interventions or procedures of the study that will be provided at no cost to subjects. – No cost to participate, all research will be performed as part of standard prostate cancer screening.
4. **In Case of Injury:**
If a patient is injured while on study, he should seek treatment and contact the study doctor as soon as he is able. Yale School of Medicine and Yale-New Haven Hospital do not provide funds for the treatment of research-related injury. If the patient is injured as a result of participation in this study, treatment will be provided. He or his insurance carrier will be expected to pay the costs of this treatment. No additional financial compensation for injury or lost wages is available.

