- The principal investigator of this study is qualified to serve as P.I. and has the support of the hospital for this research project.

YNHH HSPA Name (PRINT) and Signature _____

Date _____

For HIC Use Only

Date Approved _____

Human Investigation Committee Signature _____

This protocol is valid through _____

SECTION V: RESEARCH PLAN

1. **Statement of Purpose:** State the scientific aim(s) of the study, or the hypotheses to be tested.
Specific Aims:
1. Determine the incidence of prostate cancer in men with the BRCA2 gene mutation as an independent indicator for prostate cancer screening.
2. **Background:** Describe the background information that led to the plan for this project. Provide references to support the expectation of obtaining useful scientific data.

Prostate cancer remains the most commonly diagnosed malignancy among men with an estimated 230,000 incident cases annually in the U.S. Emphasis has been placed on overtreatment, but prostate cancer remains the most lethal malignancy for men. Genetic factors, like a family history of prostate cancer, are associated with a higher risk of developing the disease, but a connection with more aggressive disease is controversial. Recently, the BRCA mutation, commonly known for its role in breast and ovarian cancer, has been identified as risk factor for prostate cancer in men that may also confer a risk of developing more aggressive prostate cancer at a younger age. While several retrospective studies of men with prostate cancer suggest that BRCA2 mutation carriers are at significantly higher risk of developing prostate cancer at an earlier age and more advanced stage, [1-4] prospective data is lacking. Concern about whether this mutation confers more advanced disease and worse survival may contribute to significant anxiety in some men. A man in England with a BRCA2 mutation, for example, was so worried about his possible risk of prostate cancer that he had a

prophylactic surgical removal of his prostate[5]. This example clearly illustrates the key knowledge gaps that exist about the actual risk of prostate cancer among BRCA2 mutation carriers.

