We have established a multidisciplinary group of radiation oncologists, urologists, geneticists and engineers that is uniquely positioned to address this knowledge gap about the importance of the BRCA mutation and risk of prostate cancer. Our group has developed the Yale School of Medicine Fusion Prostate Biopsy Program. This program uses cutting-edge multiparametric magnetic resonance imaging (MRI) to identify previously invisible lesions in the prostate. The office-based Artemis platform (Eigen, Grass Valley CA) then “fuses” these images with 3D ultrasound to achieve more precise and accurate prostate biopsies, allowing for better clinical staging with a single biopsy. The Yale Fusion Prostate Biopsy Program has dramatically improved prostate cancer detection to more than 60%, almost twice that of the current standard of care. Through the Yale Cancer Center Genetic Counseling program, which provides genetic counseling and testing to people at increased risk for hereditary cancer, we have an established cohort of families with known genetic mutations including BRCA2.

Our study, by combining the Fusion Prostate Biopsy Program and the Genetic Counseling program to perform highly sensitive prostate biopsies in a population of BRCA2 mutation carriers, is a novel approach to accurately determine the risk of prostate cancer, adverse pathologic features and abnormal MRI findings among BRCA2 mutation carriers. While it is beyond the scope of this pilot grant, we believe that early identification of men with higher risk disease should allow for more rapid treatment and a higher likelihood of cure. We hypothesize that the BRCA-2 mutation is associated with a higher risk of prostate cancer incidence, worse grade, and abnormal MRI findings compared to patients without this mutation. To address these important questions, our specific aims are:

1. To prospectively determine the incidence of prostate cancer in BRCA2 mutation carriers.
2. To investigate different characteristics of MRI-detected prostate lesions.
3. To compare pathologic and clinical findings to clinically matched controls using the same sensitive MRI-based biopsy technique.

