Standard of care screening at the Yale Cancer Center for men with a normal prostate cancer risk consists of a PSA test and prostate physical examination beginning at age 50 years and if either is abnormal an MRI of the prostate followed by Fusion-targeted biopsy of the prostate is performed (Figures 1 and 2). Men with genetic risk factors such as African American or Caribbean heritage, a positive family history of prostate cancer, or a BRCA2 mutation, are counseled about their increased risk of prostate cancer and that prostate cancer screening (PSA and prostate exam then MRI and prostate biopsy if indicated) should begin at age 40yr but is available to them at any age.

Study participants will be identified because of their BRCA2 mutation that places them at increased risk for developing prostate cancer. Because this is a pre-selected high-risk population, and our goal is to establish the incidence of cancer and association of risk factors with developing disease, all men ≥ 30 years of age, able to give informed consent, and with at least a 5-10 year life expectancy will have PSA testing, prostate examination, Pelvic MRI, and Artemis fusion prostate biopsy (Figures 1 and 2).

Men identified to have prostate cancer will be treated according to current standards of care. Treatment for prostate cancer at the Yale Cancer Center is largely based on clinical risk; options include, but are not limited to, active surveillance for appropriate men with low risk disease, treatment with curative intent for men with localized intermediate and high risk prostate cancer, and systemic therapy for men with metastatic disease.

[figure not shown]

Figure 1. Instrument set up at Yale to perform precision imaging-guided biopsy. The prototype device of Artemis 3D biopsy tracking system. Instrument set up at Yale from Eigen (510K approved).

[figure not shown]
[figure not shown]

Figure 2. Precision image-guided biopsy. A+B) Identification of suspicious regions in two MRI sequences C) overlay of MR contoured region on realtime US view D+E) two planes of view of the 3D model generated by US and MR segmentation F) matching whole mount histology slide following prostatectomy.

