Typical clinical workflow for an Artemis MR-US fusion biopsy includes a pre-procedure MRI followed by a 12-core transrectal-ultrasound (TRUS) guided biopsy (Figure 1,2). The ultrasound transducer is fixed with a needle guide, and the biopsy needle is then guided to specific regions in the prostate gland for systematic sampling of the gland. If any areas suspicious for cancer (labeled regions of interest (ROIs)) are identified in the MRI, they are outlined using specialized software, and the target is visible on the Artemis device. Targeted biopsies will be taken from each ROI to rule out cancer in these suspicious areas.

4. **Genetic Testing** N/A

5. **Subject Population:** Provide a detailed description of the types of human subjects who will be recruited into this study.

Men \geq 30 years of age with known BRCA2 mutation and able to give informed consent.

6. **Subject classification:** Check off all classifications of subjects that will be specifically recruited for enrollment in the research project. Will subjects who may require additional safeguards or other considerations be enrolled in the study? If so, identify the population of subjects requiring special safeguards and provide a justification for their involvement.

 Children	 Healthy	 Fetal material, placenta, or dead fetus
 Non-English Speaking	 Prisoners	 Economically disadvantaged persons
 Decisionally Impaired	 Employees	 Pregnant women and/or fetuses
 Yale Students	 Females of childbearing potential	

NOTE: Is this research proposal designed to enroll children who are wards of the state as potential subjects? Yes No (If yes, see Instructions section VII #4 for further requirements)

7. **Inclusion/Exclusion Criteria:** What are the criteria used to determine subject inclusion or exclusion?

All men \geq 30 years of age with at least a ten-year life expectancy, a known BRCA2 mutation, ability to have an MRI, and able to give informed consent will be approached to participate in the study. If a man has received or is currently receiving treatment for prostate cancer he will be excluded from the study.

8. How will **eligibility** be determined, and by whom?

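### The stated aim (BRCA2 as an independent indicator, and incidence) goes beyond a one-time biopsy of carriers only, which estimates the proportion with biopsy-detected cancer

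*Combined protocol and SAP*

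**What the plan says.** Section V.1 gives the single aim: "Determine the incidence of prostate cancer in men with the BRCA2 gene mutation as an independent indicator for prostate cancer screening". The Background (V.2) states a comparative hypothesis: higher incidence, "worse grade, and abnormal MRI findings compared to patients without this mutation". Its third aim is "To compare pathologic and clinical findings to clinically matched controls using the same sensitive MRI-based biopsy technique".

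The Research Plan (V.3) adds that "our goal is to establish the incidence of cancer and association of risk factors with developing disease". The same section describes earlier screening for "Men with genetic risk factors such as African American or Caribbean heritage, a positive family history of prostate cancer, or a BRCA2 mutation", so it treats these as distinct reasons for concern.

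Section V.5 limits the population to men of at least 30 "years of age with known BRCA2 mutation and able to give informed consent". Sections V.12 and VII.1 set the number at 100. V.3 gives every participant PSA, examination, MRI and fusion biopsy. Normal-risk men at the centre go on to MRI and biopsy only when PSA or examination is abnormal.

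Section VIII, answering a question about protected health information, says: "Subject Name, date of birth, and Medical Record number as well as clinical imaging, pathologic and staging information will be collected". The Statistical Considerations (V.12) name no estimator, interval, association analysis or control group.

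**The concern.** Two words in the aim carry more than the design can bear.

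- **Independent.** The natural statistical reading is that BRCA2 matters over and above other risk factors. That needs men with and without the mutation, or at least a way to separate the mutation from what travels with it. Recruitment runs through a genetic counselling programme with a cohort of families (V.2) and through female carriers inviting male relatives (V.3). Family history may well be over-represented, although the documents give no figure.
- **Incidence.** One biopsy shows who has cancer on that day, not who goes on to develop it.

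If the wording stands, a detection proportion in carriers could be read as evidence that the mutation by itself justifies screening, or as a rate of new disease. Unless family history and heritage are recorded in the same way for everyone before biopsy, a reader cannot tell how far the proportion reflects men who already had another reason for early screening.

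**Working it through.** **1. What varies in the cohort.** Write logit P(cancer) = a + b·BRCA2 + c·family history + d·heritage. With BRCA2 = 1 for every man (V.5, V.7), only the sum a + b can be estimated. This is true at 100 men or any other number.

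**2. What one work-up measures.** Incidence is new cases divided by time at risk in men free of disease at the start. V.3 describes one work-up and gives no repeat biopsy or follow-up schedule, so there is no time in the denominator. The result is x/n, cancers found over men biopsied. V.7 excludes men who have had or are having treatment for prostate cancer, so n counts carriers without such treatment.

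**3. The plan's own figure.** V.12 gives 100 men without a formula, so it can be neither reproduced nor refuted. Base rate times fold increase gives:
- 0.01% × 4.6 = 0.046%
- 0.01% × 23 = 0.23%
- 6.5% × 4.6 = 29.9%
- 6.5% × 23 = 149.5%, which is not a possible proportion (V.12 does not itself pair these two values)

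At 4.6-fold, the expected number in 100 men runs from 0.046 to about 30. The inputs do not fix the expected yield.

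**4. What 100 men deliver.** The exact 95% interval has lower limit Beta(0.025; x, n−x+1) and upper limit Beta(0.975; x+1, n−x):

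| Cancers in 100 | Proportion | Exact 95% interval |
|---|---|---|
| 0 | 0% | 0% to 3.6% |
| 10 | 10% | 4.9% to 17.6% |
| 20 | 20% | 12.7% to 29.2% |
| 30 | 30% | 21.2% to 40.0% |

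**5. The comparator.** Aim 3 announces matched controls and V.12 does not mention them. If they came from the clinic's normal-risk men, they would have reached biopsy through an abnormal PSA or examination, whereas all carriers are biopsied. V.11 itself says some participants would otherwise have had no biopsy. The reference chosen can reverse the direction of the result. Taking 29.9% in carriers:
- against the 6.5% in V.12, the ratio is 29.9/6.5 = 4.6
- against the fusion programme's detection of more than 60% in V.2 (population not stated), it is at most 29.9/60 = 0.50

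**6. Confounding by family history (illustration; every input is assumed).** Ratio = [1 + p1(RR−1)] / [1 + p0(RR−1)], where p1 and p0 are the shares with a family history in carriers and comparators. With RR = 2:
- p1 = 50%, p0 = 15%: 1.5/1.15 = 1.30
- p1 = 80%, p0 = 10%: 1.8/1.1 = 1.64

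**7. Risk-factor goal (illustration; rates and prevalences assumed).** Suppose a factor doubles the proportion from 20% to 40% in 100 carriers. At two-sided 5%, power is 33%, 47%, 55% and 59% when 10%, 20%, 30% and 50% of men have the factor. That suits exploratory estimates with intervals, not firm conclusions.

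**The case against.** The strongest reply is that the aim speaks of an indicator for screening, not an independent risk factor. It may mean that carriage alone triggers the work-up, whatever the PSA or examination shows. That fits biopsying every man, and an all-carrier cohort can describe the yield of such a policy. The documents do not define the term, so this reading cannot be excluded. It does not remove the problem, because V.3 already names family history and heritage as grounds for earlier screening. Showing yield for carriage alone still requires reporting by those factors.

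Other parts of the reply stand and limit the point:

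- A reader might infer that there is no comparator. Aim 3 names one. The gap is that it is undefined.
- A reader might infer that family history and heritage will not be available. Section VIII answers a question about protected health information and is not a case report form. It does not name PSA either, although every man has the test. Research data come from the medical record, and medical history is reviewed for eligibility (V.8). What is missing is a commitment to record and analyse these items.
- A reader might infer that no risk-factor association can be estimated. Age and MRI findings vary among carriers and are covered by the Section VIII list. Their associations are unspecified, not impossible.
- Family history may partly reflect the mutation itself, since affected relatives may carry it. The ratios in step 6 are therefore not estimates of bias, and even 1.64 would leave 4.6/1.64 = 2.8 at the lower end of the plan's range.
- V.2 calls the work a pilot and states its own first aim without the independent-indicator wording, though it keeps the word incidence.

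**Conclusion.** The point holds as a mismatch between the stated aim and what the design estimates. Two parts rest on the documents alone: BRCA2 status is constant in the enrolled men, and no follow-up is described. The cohort therefore yields a biopsy-detected proportion, with an exact 95% interval of roughly 8 to 10 points either side when 20 to 30 cancers are found. It yields neither an incidence nor a BRCA2 effect apart from family history and heritage. The undefined controls of aim 3 do not close that gap as the plan stands.

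The possible size of confounding, 1.30 to 1.64, is illustrative and rests on assumed prevalences and an assumed doubling of risk. The documents do not support the stronger reading that both the independence claim and the risk-factor goal are beyond rescue. Nor does this point show the sample size of 100, or any other stated number, to be wrong.

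**What to change.** - **V.1:** delete the closing phrase on an independent indicator. State the aim as the proportion of BRCA2 carriers with biopsy-detected cancer, with an exact 95% confidence interval. Carry the same wording into V.2 aim 1, V.3 and V.12, where incidence also appears.
- **Data:** record family history of prostate cancer and heritage for every man at the existing consultation before biopsy. Name both as study variables.
- **Reporting:** give the proportion overall, by age and by family history.
- **V.3:** replace "association of risk factors with developing disease" with exploratory association with cancer found at biopsy, and list the factors, including age and MRI findings.

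A claim about BRCA2 in its own right would belong in aim 3, once the controls' number, source, route to biopsy, matching variables and analysis are written down. Whether to match on family history is a matter of judgement, because it may partly reflect the mutation. No particular choice is asked for here.

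The cost is a more modest claim, a few reworded sentences and two history items. No procedure, visit or participant is added.

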4. Localized prostate cancer is treatable and often curable while metastatic disease is not, hence prostate cancer screening is performed to identify patients at an earlier stage. Early detection of prostate cancer in this group of younger men at high-risk population may allow for identification while at a lower stage and grade, potentially increasing the number of patients able to receive treatment with curative intent.

All previous studies in the literature have evaluated the incidence of BRCA2 mutation carriers in a population of patients already diagnosed with prostate cancer. The incidence of prostate cancer in men with a BRCA2 mutation, however, has not been previously described.

3. **Research Plan:** Summarize the study design and research procedures using non-technical language that can be readily understood by someone outside the discipline. Be sure to distinguish between standard of care vs. research procedures when applicable, and include any flowcharts of visits specifying their individual times and lengths. Describe the setting in which the research will take place.

This is a cohort screening study to prospectively identify the incidence of prostate cancer in a population of BRCA2 carriers. All men identified to have a BRCA2 mutation as part of the Yale Cancer Genetic Counseling Program will be approached and offered participation in the study via our program newsletter, BRCA listserv, Facebook page and a targeted mailing. We will also contact all female BRCA2 carriers and ask them to invite their male relatives known to carry BRCA2 mutations into this study through the same means. For patients who test positive for a BRCA2 mutation after this study has opened, we will discuss this study with them at result disclosure and include it as part of their summary letter.

Potential participants will meet with a urologic oncologist to discuss the risks and benefits of prostate cancer screening including individual risks and benefits of PSA testing, prostate examination, pelvic MRI, prostate biopsy, and a prostate cancer diagnosis..

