Yale genetic counselors will determine initial eligibility from the BRCA2 registry to confirm the presence of a BRCA2 mutation. Trained physicians will determine clinical eligibility based on medical history.

9. **Risks:** Describe the reasonably foreseeable risks, including risks to subject privacy, discomforts, or inconveniences associated with subjects participating in the research.

Risks of prostate biopsy include: infection, rectal bleeding, blood in urine or semen, prostatitis, urosepsis, urinary retention, and potential difficulty with urination.

Magnetic resonance (MR) is a technique that uses magnetism and radio waves, not x-rays, to take pictures and measure chemicals of various parts of the body. The United States Food and Drug Administration (FDA) has set guidelines for magnet strength and exposure to radio waves, and we carefully observe those guidelines.

Patients will be watched closely throughout the MR study. Some people may feel uncomfortable or anxious. If this happens to you, you may ask to stop the study at any time and we will take you out of the MR scanner. On rare occasions, some people might feel dizzy, get an upset stomach, have a metallic taste or feel tingling sensations or muscle twitches. These sensations usually go away quickly but please tell the research staff if you have them.

There are some risks with an MR study for certain people. If someone has a pacemaker or some metal objects inside their body, they may not be in this study because the strong magnets in the MR scanner might harm them. Another risk is a metallic object flying through the air toward the magnet and hitting the participant. To reduce this risk we require that all people involved with the study remove all metal from their clothing and all metal objects from their pockets. Nothing metal can be brought into the magnet room at any time. Also, once the participant is in the magnet, the door to the room will be closed so that no one from outside accidentally goes near the magnet.

10. Minimizing Risks: Describe the manner in which the above-mentioned risks will be minimized.

Risks will be minimized using standard of care methods to limit prostate biopsy-related patient discomfort and the risk of infection through administration of local anesthetic and peri-procedure antibiotics, respectively.

FDA guidelines for MRI safety are strictly adhered to.

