 Letter	 Departmental/Center Website	 Television
 Medical Record Review	 Departmental/Center Research Boards	 Newspaper
 Departmental/Center Newsletters	 Web-Based Clinical Trial Registries	
 YCCI Recruitment database	 Clinicaltrials.gov Registry (do not send materials to HIC)	
 Other (describe):		

3. Recruitment Procedures:

- a. Describe how potential subjects will be identified.
 - i. Potential subjects will be identified through the Yale Cancer Genetic Counseling Program.
 - ii. For patients who test positive for a BRCA2 mutation after this study has opened, we will discuss this study with them at result disclosure and include it as part of their summary letter
- b. Describe how potential subjects are contacted.

- i. Potential subjects with a known BRCA2 mutation will be approached and offered participation in the study via our program newsletter, BRCA listserv, Facebook page and a targeted mailing. We will also contact all female BRCA2 carriers and ask them to invite their male relatives known to carry BRCA2 mutations into this study through the same means.
 - ii. For patients who test positive for a BRCA2 mutation after this study has opened, we will discuss this study with them at result disclosure and include it as part of their summary letter
- c. Who is recruiting potential subjects?
 - i. Trained genetic counselors will be recruiting possible subjects.

4.

Screening Procedures

- a. Will email or telephone correspondence be used to screen potential subjects for eligibility prior to the potential subject coming to the research office? Yes No
- b. If yes, identify below all health information to be collected as part of screening and check off any of the following HIPAA identifiers to be collected and retained by the research team during this screening process.

HEALTH INFORMATION TO BE COLLECTED:

HIPAA identifiers:

Names

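### The detection rate will describe known, clinic-identified BRCA2 carriers without treated prostate cancer who want screening, but the aim applies it to all men with the mutation

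*Combined protocol and SAP*

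**What the plan says.** Section V.1 gives the aim as "Determine the incidence of prostate cancer in men with the BRCA2 gene mutation as an independent indicator for prostate cancer screening". It does not limit the population by how a man was found to carry the mutation. The aims in V.2 are equally general, and V.2 says the design will give an accurate risk for carriers.

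The route into the study is narrower:

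- **Source.** V.2 describes a counselling programme "which provides genetic counseling and testing to people at increased risk for hereditary cancer". V.3 says "All men identified to have a BRCA2 mutation as part of the Yale Cancer Genetic Counseling Program will be approached and offered participation", with contact "via our program newsletter, BRCA listserv, Facebook page and a targeted mailing".
- **Relatives.** Female carriers are contacted, and the programme will "ask them to invite their male relatives known to carry BRCA2 mutations into this study" (V.3, repeated in VII.3).
- **Eligibility.** V.8 says "Yale genetic counselors will determine initial eligibility from the BRCA2 registry to confirm the presence of a BRCA2 mutation". V.7 excludes men with past or current treatment for prostate cancer.
- **Consent.** Under VII.9 the study is described at an office visit to eligible men who want to be screened.

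V.2 names family history of prostate cancer as a risk factor, and V.3 lists it beside the BRCA2 mutation. V.12 states the purpose, a 4.6 to 23 fold risk, a normal-risk detection range of 0.01% to 6.5%, and 100 men. It gives no estimator, interval, subgroup or account of men approached. The data named in Section VIII are identifiers plus imaging, pathology and staging information.

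**The concern.** A man is a known carrier here because he or a relative came to a service for hereditary cancer. He contributes data only if he has not been treated for prostate cancer and wants screening. Each step can change the share of men with cancer, and none is part of the population named in the aim.

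The claim that BRCA2 is an indicator in its own right is the most exposed. If participants have more prostate cancer in their families than carriers in general, part of a pooled rate belongs to family history, which the protocol itself treats as a separate factor. Neither family history nor source is on the data list, so a reader of the results could not separate the two. The study is meant to inform screening of carriers, and a crude rate from this sample would be taken as the risk conferred by the mutation.

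**Working it through.** **The plan's own figure.** V.12 says 100 men follows from its fold risks and baseline rates. It cannot be reproduced from them. The products are 4.6 × 0.01% = 0.046%, 23 × 0.01% = 0.23%, 4.6 × 6.5% = 29.9%, and 23 × 6.5% = 149.5%, which is impossible. No error rate, power or precision target is given. The nearest match is a half-width of 10 points at 50%: 1.96² × 0.25 / 0.10² = 96.04, so 97 men. The protocol states no such target. The sample size therefore says nothing about which population is meant.

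**Inputs for the bias.** The documents give no share of men with a family history, no relative risk for it, and no share of cases already treated. All of these are assumptions here, as is a true rate p = 20% among all carriers.

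**Upward effect of family selection.** Let f_s and f_p be the shares with a prostate-cancer family history among participants and among all carriers, and RR the relative risk. Then

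u = [1 + f_s(RR − 1)] / [1 + f_p(RR − 1)].

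- RR 1.5, f_s 0.3, f_p 0.1: 1.15 / 1.05 = 1.095
- RR 2, f_s 0.5, f_p 0.2: 1.5 / 1.2 = 1.25
- RR 3, f_s 0.7, f_p 0.3: 2.4 / 1.6 = 1.50

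**Downward effect of the exclusion.** Let d be the share of cases already treated and therefore excluded. The observed rate is p(1 − d) / (1 − pd). At p = 20% this gives 18.4% (0.92 times) for d = 10%, 15.8% (0.79 times) for d = 25%, and 11.1% (0.56 times) for d = 50%.

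**Both together.** Put p_s = 20% × u in place of p in the second formula and divide by 20%:

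| Family selection | d = 0 | d = 10% | d = 25% | d = 50% |
|---|---|---|---|---|
| RR 1.5, 0.3 vs 0.1 | 1.10 | 1.01 | 0.87 | 0.62 |
| RR 2, 0.5 vs 0.2 | 1.25 | 1.15 | 1.00 | 0.71 |
| RR 3, 0.7 vs 0.3 | 1.50 | 1.39 | 1.22 | 0.88 |

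The two effects cancel when d = (p_s − p) / [p_s(1 − p)]. For the three rows this is about 11%, 25% and 42%. Nothing in the documents says which side of these values applies.

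**What the pooled rate hides.** In the middle row with d = 0, the sample rate is 25%. The rate without family history is 25% / (1 + 0.5 × 1) = 16.7%, and with it 33.3%. A pooled 25% credited to BRCA2 would describe neither group.

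**Would the interval show it?** With 20 cases in 100 the exact 95% interval is 12.7% to 29.2%, a half-width of about 8 points. A shift from 20% to 25% lies inside it. A confidence interval covers sampling error only, and more men recruited by the same routes would not remove the shift.

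**Precision after stratifying.** If half the men fall in a stratum (an assumption), 10 cases in 50 gives an exact interval of 10.0% to 33.7%.

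**The case against.** The best defence is that the gap is smaller than it looks. V.5 and V.7 already restrict the study to known carriers, and a screening indicator can be used only in men whose mutation is known. For that use, men already treated are rightly outside the target, so their exclusion defines the population and does not bias the rate. V.3 calls the participants a selected high-risk group and mentions studying risk factors. V.2 plans a comparison with matched men. The study is described as a pilot, and its data come from the medical record, where family history may well be found.

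Much of this stands, and it points to the population that should be named. It does not repair the plan. V.3 attributes the selection to the mutation, not to how families came to be tested. The risk-factor goal and the matched comparison are not carried into V.12, and no matching on family history is stated. Being retrievable from a record is different from being planned, and nothing provides for a count of men approached.

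A reader might go further and infer that the rate overstates risk. The documents do not support that. The clinic serves hereditary cancer in general, and V.2 notes that BRCA is best known for breast and ovarian cancer. No share of families with prostate cancer is given, volunteers could differ in either direction, and the exclusion works downwards for carriers as a whole.

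A reader might also infer that unregistered web volunteers enter the study. Web posting and mass e-mail are ticked in VII.2, but V.3, V.8 and VII.3 present these as ways to reach men identified by the programme, with carrier status checked in its registry. Contact channel is not source.

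**Conclusion.** The concern holds as a mismatch between the population sampled and the population named. The pooled rate will apply to known carriers found through a cancer-genetics programme, or invited as relatives, who have no treated prostate cancer and are willing to be screened. V.1 and V.2 apply it to men with the mutation at large and treat the mutation as an indicator in its own right, without data on the competing family factor.

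The net direction and size cannot be determined. Over the assumed inputs, the ratio of observed to true rate runs from 0.62 to 1.50 and passes through 1.00. The upward part rests on participants having more family history than carriers generally. The downward part applies only if the target includes men already treated. The case for change does not depend on these numbers: the passages on aim, source, exclusion and data collection do not match.

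**What to change.** 1. In V.1 and V.2, state the target population as known BRCA2 carriers identified through a cancer-genetics programme, or as their invited relatives, without treated prostate cancer. Acknowledge that they are men willing to be screened.
2. Add two items to the collected data: each man's family history of prostate cancer, and his source (carrier identified by the programme, or relative invited by a female carrier).
3. In V.12, report the detection rate with exact 95% intervals overall, by family history and by source. Give the numbers approached, eligible and enrolled.
4. Describe the rate as independent of family history only if the stratum without family history supports it, by a criterion written down beforehand.

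Weighting the rate to the registry is not advised. It would address non-participation but not selection into the clinic, and it needs registry family-history counts that the documents do not show to exist. It would also be unstable with 100 men.

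The cost is two data fields, a recruitment log and a few lines of text. Study procedures and sample size stay the same. The downside is a narrower stated target and wide intervals within strata, so the stratified results will be descriptive.
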